#### 4.2. Sensitivity to imbalance in baseline covariates

Randomization is important to ensure that the treatment arms are balanced at baseline. Although subjects in the Prospective Confirmatory Data Cohort were randomized, this randomization took place prior to the identification of the baseline NT-proBNP subgroup. As such, it may be possible that there are imbalances in the treatment arms with respect to baseline variables in the subgroup. To mitigate the potential impact of any imbalances, a propensity score analysis will be performed to adjust for observed imbalances in the treatment arms with respect to observed baseline characteristics.

Propensity scores will be estimated using logistic regression with randomized arm as the dependent variable and a pre-specified list of baseline characteristics that may be related to variation in endpoint data as independent variables. Propensity scores will be used in an inverse probability of treatment weighted (IPTW) model, such that all patient data will be included in the analysis. As weights may be unstable for patients with a low or high propensity score, a maximum weight will be specified. The analysis will use average treatment effect in treated subjects (ATT) weights for the weighted analysis and standardized differences to assess the degree of imbalance between baseline variables. ATT weights and standardized differences have been defined in Austin (2011). Baseline variables will be considered suitably balanced if the standardized difference is less than 0.1. For each endpoint, propensity score weights will be used to perform a weighted version of the primary regression analysis defined for that endpoint in order to estimate a propensity-score adjusted treatment effect.

The following baseline covariates will be included in the IPTW: Gender, age (<65 year vs ≥65 years), race, NT-proBNP, 6MHW, history of heart failure hospitalization, history of either CABG, MI or atrial fibrillation.

#### 4.3. Intention-to-Treat Analysis

To assess the potential for bias in the comparison of the treatment arms due to differences in withdrawal during follow-up, a sensitivity analysis will be performed on all randomized subjects in which follow-up time will begin at time of randomization, instead of “activation” [defined as actual device implant (device subjects) or anticipated implant date that is recorded prior to randomization (medical management subjects)]. All events that occur from time of randomization will be included in the analysis, even the events in subjects that have no post-activation follow-up.

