## 3. PRIMARY AND FOCUSED ENDPOINTS

### 3.1. Primary Endpoint: Rate of CV Mortality and HF Morbidity

#### 3.1.1. Rate of Cardiovascular Mortality and Heart Failure Morbidity

The objective is to demonstrate that treatment with the BAROSTIM NEO System, relative to medical management, reduces the rate of cardiovascular mortality or worsening heart failure that leads to hospitalization or emergency room visit, cardiac assist device or heart transplant.

Subjects will be censored at the time of a terminal event (i.e., death, permanent cardiac assist device, heart transplant, or novel implantation of a device to receive Cardiac Contractility Modulation) or end of follow-up, whichever occurs first.

The end of follow-up for analysis of morbidity and mortality will occur on the last date where adverse event status is known for the subject. This definition of follow-up time ensures that only time periods where morbidity and mortality status has

been assessed are included. End of follow-up is defined for each subject as the later date of:

- Last study visit
- Last date of adverse events reported in the database:
  - If last adverse event is a hospitalization, use discharge date
  - If last event is not a hospitalization, use resolution date if resolved, else use onset date
- Date subject completed the final, protocol defined end of study visit (note: this only occurs at end of study)

This end of follow-up date will be used to calculate follow-up time for the negative binomial model.

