#### 3.1.5. Analysis Population

The analysis population for the prospective data to be analyzed for this endpoint is all randomized subjects with a baseline NT-proBNP < 1600 that have post-activation follow-up. Endpoint follow-up evaluation for the morbidity and

mortality endpoint begins at the actual device implant (device subjects) or anticipated implant date that is recorded prior to randomization (medical management subjects). All events adjudicated by the CEC as meeting the endpoint event definitions will be included in the analysis. Both prospective and previously analyzed follow-up time periods and events will be included in the analysis.

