- An analysis that counts all specified therapeutic interventions as events contributing toward the endpoint, with follow-up time accruing until last available contact/death.
- An analysis imputing events for the post-therapeutic intervention period, separately for the randomized arms. Imputation will be based on subject's baseline covariates and pre-therapeutic intervention data and the amount of follow-up time available post-therapeutic intervention. For this sensitivity analyses, these imputed events will be considered as an event contributing toward the endpoint.

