## 5.3. Alternative Statistical Methods for Analyzing Rates

To further incorporate the impact of the timing that the events occur over follow-up, alternative methods of analysis on the endpoints will be performed. These will include, at a minimum, the Anderson Gill method for recurrent events, and semi-parametric joint frailty models (JFM).

The JFM analysis is intended to aid the interpretation of the primary negative binomial model analysis by providing insight into the contribution of censoring events and recurrent heart failure hospitalization events to the overall (marginal) treatment effect estimated by the negative binomial model analysis. This JFM has a demonstrated ability to provide unbiased estimate of the treatment effect on recurrent heart-failure hospitalizations in the presence of dependent censoring (i.e., censoring being more likely in subjects at higher risk of heart-failure hospitalization). In the JFM, the dependence of censoring and recurrent events is accounted for by a frailty term, which measures a patient-specific tendency to have an increased likelihood of both types of events. The model assumes that a patient's censoring and recurrent events are independent of each other after conditioning on the frailty term. The JFM will be implemented using piecewise constant hazards for the recurrent events and censoring events. This method may be implemented by Gaussian quadrature using SAS PROC NLMIXED24. Piecewise constant hazard time intervals will be defined prior to performing analyses comparing treatment arms. For each hazard ratio comparing the two arms, a 95% confidence interval and p-value will be calculated using the Wald method. The JFM analysis will be repeated with only death as a dependent censoring event and transplant/LVAD as non-informative censoring events.

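### SAP 4.3 is offered as a test of bias from withdrawal during follow-up, but it tests only exclusions before activation, and no other planned analysis expressly treats withdrawal as informative

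*SAP*

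**What the plan says.** **Purpose.** SAP 4.3 opens: "To assess the potential for bias in the comparison of the treatment arms due to differences in withdrawal during follow-up".

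**Method.** The section then makes three changes to the primary analysis:
- The clock: "follow-up time will begin at time of randomization, instead of" activation, which means the actual implant date for device subjects and the anticipated implant date for controls.
- The population: all randomized subjects. The primary set in SAP 3.1.5 is "all randomized subjects with a baseline NT-proBNP < 1600 that have post-activation follow-up".
- The events: "All events that occur from time of randomization will be included in the analysis, even the events in subjects that have no post-activation follow-up".

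**What stays the same.** SAP 3.1.1 says that the end of follow-up "will occur on the last date where adverse event status is known for the subject". Section 4.3 does not alter this.

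**Nearby analyses.** SAP 5.3 plans a joint frailty model for dependent censoring and adds: "The JFM analysis will be repeated with only death as a dependent censoring event and transplant/LVAD as non-informative censoring events". The list after Table 3 in SAP 4.1 includes "An analysis imputing events for the post-therapeutic intervention period, separately for the randomized arms". The introduction to SAP Section 4 says that its morbidity and mortality sensitivity analyses replace those of the main SAP.

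**The concern.** The bias named in 4.3 arises at the back end of follow-up, when subjects leave and their later events go unseen. The method works at the front end. A result from 4.3 that agrees with the primary analysis could be read as showing that withdrawal did not matter, although it says nothing about withdrawal after activation.

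The threat is a plausible one here. Controls receive no implant, so subjects and sites know the arm. Protocol 3.4.1 lists minimizing withdrawal among its instructions to reduce bias. Protocol 3.12 names receiving a BAROSTIM NEO implant, where it is marketed, as a possible reason for withdrawal. If the primary result is close to its boundary, the reader needs to know how much adverse experience in the unobserved time would overturn it. The plan does not provide that.

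**Working it through.** **1. How far 4.3 can move the result**

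I read 'all randomized subjects' as those in the NT-proBNP subgroup.
- Subjects: SAP Section 1 gives 319 analysed plus 4 never implanted = 323, so 4/319 = 1.3% more. (The 259 earlier and 59 later subjects sum to 318, one below 319; I use the stated figures.)
- Time: Protocol Table 6 allows 14 days from randomization to implant, or 28 with a proctor. Protocol 4.3.3 expects 2.3 years of follow-up, about 840 days. 14/840 = 1.7%; 28/840 = 3.3%.

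**2. Whether another analysis fills the gap**

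| SAP section | What it does | Reaches withdrawal after activation? |
|---|---|---|
| 4.1 | Censors at, counts, or imputes after a Table 3 intervention | Only where withdrawal accompanies such an intervention, and imputation uses the follow-up time available afterwards |
| 4.4 | Adds censoring at device-off or crossover | No |
| 5.2 | Truncates at 6, 12 and 24 months | Limits late loss; does not model it |
| 5.3 | Joint frailty model; names death and transplant/LVAD | Not named |
| 3.2.2 | Win ratio on shared follow-up; imputes quality of life | Equalises duration; does not model why follow-up ended |

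**3. Standard error from the SAP's own figures**

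Table 2 requires an observed reduction of at least 28% (rate ratio 0.72). Table 7 gives a final boundary of 2.4335, whose one-sided tail is 0.0075, matching the nominal p-value printed there.

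SE = −ln(0.72)/2.4335 = 0.3285/2.4335 = 0.135

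An observed rate ratio of 0.65 then has Z = ln(0.65)/0.135 = −3.19.

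**4. Illustration: loss in the device arm**

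Assume a share w of device-arm time is unobserved and ran at the control rate, with the SE held fixed:

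RR_adj = (1 − w) × RR_obs + w

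- w = 0.15: 0.85 × 0.65 + 0.15 = 0.7025, Z = −2.62, still past the boundary.
- w = 0.20: 0.80 × 0.65 + 0.20 = 0.72, Z = −2.43, on the boundary.
- Solving for 0.72: w = (0.72 − 0.65)/(1 − 0.65) = 0.20.

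**5. Illustration: loss in the control arm**

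Assume 5% of control time is unobserved and ran at twice the observed control rate. The control rate rises by the factor 1 + 0.05 × (2 − 1) = 1.05, so the rate ratio becomes 0.65/1.05 = 0.619 and Z = −3.55. The result strengthens.

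**6. Simulation of the 4.3 clock**

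Settings: 319 subjects, 2.3 years each, control rate 0.4, observed-period rate ratio 0.65, gamma frailty with shape 1.7, and 14 pre-activation days at the control rate in both arms. Withdrawal was in the device arm only, at mid-follow-up. Covariates, terminal events and the four never-implanted subjects were left out. The table shows median rate ratios over 300 replicates.

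| Withdrawn; later event rate | Primary | 4.3 clock | Complete follow-up |
|---|---|---|---|
| None | 0.655 | 0.662 | 0.655 |
| 10%; doubled | 0.658 | 0.669 | 0.694 |
| 20%; doubled | 0.660 | 0.667 | 0.728 |
| 20%; tripled | 0.650 | 0.656 | 0.781 |

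The 4.3 clock stays within about 0.01 of the primary estimate in every row. The complete-follow-up value departs from the primary by up to 0.13.

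**The case against.** **A reader might infer that 4.3 only moves the clock.** It does not. It restores the four never-implanted device subjects, the only arm-specific loss that the documents quantify, and counts events before activation. As a test of exclusions before activation it is sound.

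**Withdrawal does not automatically end observation.** Protocol 3.4.5 and 3.12 offer partial withdrawal with continued endpoint collection from records and contacts. Protocol 3.13 keeps lost subjects open in the database, and SAP 3.1.1 ends time when status becomes unknown, not when visits stop. This stands, and it shrinks the unobserved time. But partial withdrawal depends on the subject's agreement, and those who decline leave fully. It reduces missing data without testing the remainder.

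**A reader might infer that the plan ignores dependent censoring or excludes withdrawal from the frailty model.** The text does not support that. SAP 5.3 describes dependent censoring in general terms, does not list the censoring events of its first run, and nowhere rules withdrawal out. What can be said is that it names only death and transplant/LVAD, and that the examples in 5.4 are likewise terminal clinical events.

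**Section 4.1 partly reaches one route.** Table 3 includes non-protocol BAROSTIM implantation, which Protocol 3.12 also gives as a reason for withdrawal. That helps while follow-up continues; a subject who leaves fully at that point has no later time to impute into.

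**The trial is not open at every level.** Subjects and sites know the arm, but Protocol 5.3 keeps the Clinical Events Committee blinded.

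**The magnitude is hypothetical.** This stands. The 20% case lies on the boundary, so the third decimal of the standard error decides it, and any result already at the boundary fails under almost any adverse shift.

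**Conclusion.** SAP 4.3 claims a property that it lacks. It tests the start date and exclusions before activation; it cannot respond to withdrawal after activation. No other planned analysis expressly does so, and the main SAP cannot supply one for this endpoint because Section 4 replaces its sensitivity analyses.

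The primary test and decision rule are unaffected. A reader might go further and infer that withdrawal has biased the result in favour of the device. The documents do not support that: they give no withdrawal rate by arm, and the direction depends on which arm loses informative time.

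The size can only be illustrated. With SE about 0.135, an observed rate ratio of 0.65 reaches the boundary if about 20% of device-arm time is unobserved and ran at the control rate; at 15% it does not. These shares, the control-rate assumption and the fixed SE are assumptions, not figures from the plan.

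**What to change.** 1. Restate the purpose of 4.3 as a test of the start date and of never-activated subjects.
2. Report withdrawals and lost person-time by arm, timing and reason.
3. State in 5.3 which censoring the joint frailty model treats as dependent, and add a run with withdrawal as dependent censoring.
4. Add a withdrawal sensitivity analysis. For subjects in either arm whose follow-up ends before the endpoint closing date without a terminal event, multiply impute events to that date, with an imputed terminal event ending follow-up:
   - (a) at the subject's own-arm rate;
   - (b) with device subjects at the control rate;
   - (c) with rate multipliers set separately by arm, reporting the tipping point at which Z no longer crosses the boundary.

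The cost is SAP wording and analysis work, with no new data. The imputation in 4.1 is a starting point but needs extending: it relies on follow-up time after the intervention, which fully withdrawn subjects do not have.

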#### 4.4. Per Protocol Analysis

A sensitivity analysis will be performed with events and follow-up censored at the first time a subject receives therapy out of compliance with the protocol. For device arm subjects, the date that device therapy is turned off will be the censoring date. For medical management arm subjects, if crossover occurs, the date that device therapy is turned on will be the censoring date.

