### **3.14. Discontinuation of Therapy**

Circumstances may arise during the trial that require the device to be temporarily or permanently turned off for a subject. This may include an adverse event, an intercurrent illness or other medical condition where continued therapy would not be in the best interest of the subject, or subject's wish.

If the device is turned off temporarily, the reason should be clearly noted in the subject's medical records and a Programming CRF should be completed to document the date.

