### **3.15. Cardiac Assist Device or Heart Transplant**

Subjects in either treatment arm who progress in their heart failure status to receive either a cardiac assist device or a heart transplant must be withdrawn from the study. For subjects with an active BAROSTIM NEO device in geographies where the device is not approved, the device must be permanently turned off prior to the cardiac assist device or heart transplant procedure (see Section 3.10). The investigator should discuss the options for either leaving the IPG in place or for explanting the IPG including the potential risks of each. It is recommended that the Carotid Sinus Leads should not be explanted, and the leads should be left implanted with the leads capped. These device subjects must be followed for 30 days after the termination of device therapy or after the explanting of any of the BAROSTIM NEO System.

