### **5.11. Reduction of Heart Failure Mortality and Heart Failure Morbidity**

The morbidity and mortality endpoint will be repeated with a revised definition for the terminal events that contribute to the event count outcome in the analysis. Only mortality events where the cause of death is heart failure will be counted as death endpoint events. All other deaths are censoring events, but not counted as primary endpoint events. The LVAD, heart transplant and heart failure morbidity events are treated the same as the main primary analysis (i.e., included in the analysis as primary events).

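### The per-protocol rule in SAP 4.4 makes no exception for a protocol-required turn-off before an assist device or transplant, so such endpoint events can be lost from the device arm only

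*SAP*

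**What the plan says.** SAP 4.4 defines a sensitivity analysis with "events and follow-up censored at the first time a subject receives therapy out of compliance with the protocol". It then gives one date rule per arm. Device arm: "For device arm subjects, the date that device therapy is turned off will be the censoring date". Medical management arm: "For medical management arm subjects, if crossover occurs, the date that device therapy is turned on will be the censoring date". Neither rule refers to the reason for the change or to whether it is permanent. The introduction to SAP Section 4 commits to running these sensitivity analyses on the primary endpoint.

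Protocol 3.15 covers subjects who progress to an assist device or transplant. For a subject with an active device "in geographies where the device is not approved", it says that "the device must be permanently turned off prior to the cardiac assist device or heart transplant procedure".

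Both procedures are components of the primary endpoint, whose aim in SAP 3.1.1 is to show that the device "reduces the rate of cardiovascular mortality or worsening heart failure that leads to hospitalization or emergency room visit, cardiac assist device or heart transplant". SAP 5.11 confirms that they count as events: "The LVAD, heart transplant and heart failure morbidity events are treated the same as the main primary analysis".

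Protocol 3.14 adds a separate route to turn-off: "Circumstances may arise during the trial that require the device to be temporarily or permanently turned off for a subject".

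**The concern.** The opening sentence of SAP 4.4 and its device-arm date rule give different answers for one type of subject. A turn-off made because Protocol 3.15 requires it is in compliance, so the opening sentence would not censor. The date rule, taken as written, would. Protocol 4.1 does not settle this, because it lets the SAP override the protocol on analyses.

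If the date rule is followed, the censoring is informative and one-sided. The turn-off happens because an endpoint event is about to happen. In the device arm it can remove that event. In the control arm no censoring trigger is tied to the procedure, so the event stays. A per-protocol analysis is read as a check on the primary result among subjects treated as assigned, and part of any agreement it shows should not come from its own censoring rule.

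**Working it through.** The documents state no figure for the per-protocol analysis, so there is none to reproduce. The check has two parts.

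**1. The rules applied to the same event in each arm**

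- *Device subject, device not approved locally, transplant on day D, device turned off on an earlier day.* Protocol 3.15 is followed. The SAP 4.4 date rule censors at the turn-off. The transplant falls after censoring and does not count. A heart failure admission that began before the turn-off still counts.
- *Same subject, turn-off also on day D.* SAP 4.4 does not say whether an event on the censoring date counts, so the result is undefined.
- *Control subject, transplant on day D.* No crossover, so no per-protocol censoring. The transplant counts.
- *Primary analysis, either arm.* SAP 3.1.1 censors at the terminal event itself, and the procedure counts.

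Loss on the literal reading therefore requires a turn-off dated before the procedure.

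**2. Size**

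Inputs from the documents: fraction of events that are terminal, 0.18; control rate, 0.4 per patient-year; target rate ratio, 0.65; 331 planned subjects; dispersion 1.7 (all SAP 8.1); 320 events (SAP 3.1.3); average follow-up 2.3 years (Protocol 4.3.3); 1:1 allocation (Protocol 3.4.10). The 1.7 is read as a gamma shape, because the large-overdispersion scenario in SAP Table 4 uses the smaller value 1.4.

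Assumed, because the documents do not give it: q = s × g, where s is the share of device-arm terminal events that are assist devices or transplants, and g is the share of those with an earlier-dated turn-off.

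A fraction 0.18 × q of device-arm events is lost. If the gap between turn-off and procedure is short, follow-up barely changes, so

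apparent rate ratio ≈ true rate ratio × (1 - 0.18q).

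With no effect, about 320 / 2 = 160 events fall in the device arm, of which 0.18 × 160 = 28.8 are terminal. That is the upper limit on terminal events that could be lost.

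| q | multiplier | true 1.00 reads | true 0.65 reads | device events lost (28.8 × q) |
|---|---|---|---|---|
| 0.025 (e.g. s = 0.10, g = 0.25) | 0.9955 | 0.996 | 0.647 | 0.7 |
| 0.10 | 0.982 | 0.982 | 0.638 | 2.9 |
| 0.35 | 0.937 | 0.937 | 0.609 | 10.1 |

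A simulation on these inputs (turn-off one day before the procedure, 400 runs per setting, crude rate ratios, no true effect) agrees. For q = 0.025, 0.125, 0.25 and 0.50 the ratio of the per-protocol to the uncensored rate ratio was 0.996, 0.978, 0.955 and 0.908. The formula gives 0.996, 0.978, 0.955 and 0.910.

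For scale, the standard error of the log rate ratio with no effect, 331 / 2 = 165.5 subjects per arm and k = 1/1.7 = 0.588:

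variance = 2 × [1/(2.3 × 0.4) + 0.588] / 165.5 = 2 × (1.087 + 0.588) / 165.5 = 0.0202; standard error = 0.142.

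The log shifts are ln 0.9955 = -0.005, ln 0.982 = -0.018 and ln 0.937 = -0.065, or about 0.03, 0.13 and 0.46 standard errors.

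**The case against.** The best defence is that the opening sentence of SAP 4.4 governs, and the two arm-specific sentences only say which date to use once non-compliance has occurred. On that reading a turn-off under Protocol 3.15 never censors. The reading is reasonable, but the SAP does not state it, and a programmer implementing the device-arm sentence would censor. The defence shows that the section conflicts with itself; it does not resolve the conflict.

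Four further points stand and limit the concern:

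- The turn-off may fall on the day of the procedure, so loss is not certain even on the literal reading.
- The requirement applies only where the device is not approved. Protocol 3.12 and Section 7 show market approval in some countries and commercial availability, so few subjects may be affected. The number is not given.
- This is one sensitivity analysis with no success criterion. The primary analysis and the intention-to-treat analysis in SAP 4.3 do not censor at turn-off, so an artefact would appear as a divergence from them.
- Some asymmetry is unavoidable: controls have no device to turn off, and crossover is their natural counterpart.

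A reader might also infer that temporary turn-offs under Protocol 3.14 add to the bias because heart failure events cluster around them. The documents do not support this. Protocol 3.14 names an adverse event, another illness or condition, and the subject's wish, and says nothing about event rates around a stop. Censoring there removes person-time as well as events, so even the direction is not established.

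**Conclusion.** The concern holds as an unresolved conflict within SAP 4.4 that, read literally, loses assist-device and transplant events from the device arm only, whenever the turn-off is dated before the procedure. The resulting bias favours the device.

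Its size cannot be determined from the documents. It rests on q, which is assumed, and on a short gap between turn-off and procedure. Over q from 0.025 to 0.35 the rate ratio is multiplied by about 0.996 to 0.94, a shift of less than half a standard error. The near-zero end is as compatible with the documents as the upper end.

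Two stronger conclusions are not supported. A reader might infer that these events will drop out; the documents support only that they can, given an earlier turn-off date and the literal reading. A reader might also infer that the rule could by itself produce an apparent benefit; shifts of this size are small against the sampling error, and the primary analysis is untouched. The point still merits correction, because the analysis is committed and the remedy is a wording change.

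**What to change.** In SAP 4.4, state that:

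1. a turn-off made for an assist device or transplant is not a censoring event;
2. the procedure then counts as the endpoint event on its own date, as in the control arm;
3. events on the censoring date count.

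Report the number of device-arm subjects to whom this applies.

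For temporary turn-offs under Protocol 3.14, counting all off-time as on-treatment is a trade-off rather than a correction. At most, show the result both with and without censoring at a turn-off that was followed by reactivation.

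This changes the analysis rule only. No change to when the device is turned off is proposed.

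Cost: a few lines of SAP text. The per-protocol analysis already needs turn-off dates. Linking a turn-off to a procedure may need a look at source records for some subjects, since Protocol 3.14 puts the reason for a temporary stop in the medical record and uses the Programming CRF to document the date. The per-protocol estimate may become slightly less favourable to the device.
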